Study Protocol and Statistical Analysis Plan

Title of Study: Parent Resource About Pediatric Clinical Trials

ClinicalTrial.gov Identifier: NCT07233967

Principal Investigators: [name]; [name]

Date of Document: 05/19/2025

Table of contents

	Page number
Study Protocol	3
Objectives	3
Design	3
Methods	4
Statistical Analysis Plan	7

Study Protocol

Objectives:

To develop and test the effectiveness and safety of medical and behavioral treatments for children and adolescents, pediatric clinical trials are needed. However, some clinical trials experience difficulty with recruitment of families due to a number of reasons, such as time or travel limitations, potential risks to child, mistrust, or lack of information. Providing relevant and high-quality information to parents can positively contribute to decision-making as well as recruitment and enrollment in future clinical trials. The Pediatric Clinical Trials (PCT) Pocket Guide is an interactive, online resource designed to increase parents' awareness and understanding of clinical research and their ability to communicate with others about research, and willingness to participate in a clinical trial. The objective of this project is to examine the feasibility of the PCT Pocket Guide in a randomized controlled trial with parents of children between the ages of 7 and 17 years. Parents will complete pre- and posttest assessments, which will provide information on the acceptability, appropriateness, and feasibility of the PCT Pocket Guide and a preliminary test of the Pocket Guide's efficacy for improving outcomes related to knowledge, attitudes, self-efficacy, trust, and willingness and likelihood of participating in pediatric clinical trials.

Design:

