- a. Participants in the intervention group will then be provided via email/text with a link to access the resource (PCT Pocket Guide). They will be asked to review the resource within two weeks.
- b. Participants in the active control group will be provided via email/text with a link to access the control materials [articles and videos compiled from a NIH-supported website (Children and Clinical Studies) into one online resource]. They will be asked to review the resource within two weeks.

Project staff members will monitor resource usage by groups through the LMS. Parents who complete the resources within 2 weeks will receive a \$25 gift card. Approximately two weeks after completing the pretest questionnaire, participants will receive an email and text with a link to access to their online posttest questionnaire. This questionnaire will include the same questions and instructions at pretest as well as consumer satisfaction questions. If the parent completes the questionnaire, they will receive a \$30 gift card. Participants will receive automatic email/text reminders from the study management system if they have not completed the questionnaires or not accessed their assigned online resource.

Measures.

Implementation

The Learning Management System (LMS) will record the amount of time that participants spend with the parent resource (PCT Pocket Guide; active control) and the specific components that were reviewed.

Consumer Satisfaction

Data will be collected on participant feedback about the resource they review through a posttest consumer satisfaction questionnaire (CSQ). The CSQ will consist of the Acceptability of Intervention Measure (AIM), Intervention Appropriateness Measure (IAM), and Feasibility of Intervention Measure (FIM), which are 4 items each using a 5-pt. Likert scale (1=Completely disagree to 5=Completely agree) and have good discriminant validity and reliability (Weiner et al., 2017). Higher scores indicate greater acceptability, appropriateness, and feasibility. Participants will also be asked to rate their satisfaction with the resource's content, format, and usability using a 5-point Likert scale (1 = Strongly disagree to 5 = Strongly agree) with higher

scores indicating greater satisfaction with the resource. Participants will also respond to open-ended questions about what they liked best and least and any suggestions for changes for their assigned resource.

Outcomes

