Likelihood of participation in clinical trials. Parents will be asked to respond to one question about the likelihood of allowing their child to participate in a clinical trial (i.e., “If your child were asked to be in a clinical trial, how likely would you be to let them participate?”) and will respond using a 5-point Likert scale (1 = Not likely at all; 2 = Not very likely; 3 = Moderately likely; 4 = Very likely; 5 = Extremely likely). Parents will also be asked to respond to one question about the likelihood of their fear preventing them from allowing their child participate in a clinical trial (i.e., “How likely is it that your fearful or anxious feelings could stop you from allowing your child to participate in a clinical trial in the future?”). Parents will respond using a 5-point Likert scale (1 = Not likely; 2 = Somewhat likely; 3 = Moderately likely; 4 = Very likely; 5 = Extremely likely).

Willingness to participate in a clinical trial. Parents will review up to five research protocols related to a fictitious disease (‘meditis’) and respond to questions about their willingness to let their child participate in each research study (i.e., “If your child had meditis, would you agree to enroll them in this study?”; 1 = Definitely not to 7 = Definitely yes; and “If you had to say for sure, what would your answer be?”; 0 = No; 1 = Yes). Parents can also describe the reason for their decision in an open-ended space. Parents will also be asked about decision-makers in the decision to participate (i.e., “Who should make the final decision on whether or not your child will participate in this research study?”; 1 = my child; 2 = mostly my child; 3 = joint decision; 4 = mostly me; 5 = me). The final two questions will ask about the risk and benefits of participating in each study (i.e., “Overall, how risky is this study for your child?”; “Overall, how beneficial is this study for your child?”; 1 = Not at all to 7 = Extremely). This measure is adapted from Brody et al. (2005).

Knowledge. This measure will be created for the purposes of this study based on the content in the parent resource. Parents will respond to fact-based questions in multiple choice format that assess their knowledge about clinical research (e.g., “What does giving assent mean?”; “Once your child agrees to be in a clinical trial, can they stop before the trial is over?”).

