Main Analyses. Parents’ reports on the acceptability (AIM), appropriateness (IAM), and feasibility (FIM) of both the intervention (PCT Pocket Guide) and active control (NIH-supported website materials) will first be examined through descriptive statistics. Group mean scale scores greater than 3.0 will indicate more than a moderate amount of acceptability, appropriateness, and feasibility for each resource. Next, ANCOVAs will be used to compare AIM, FIM, and IAM scores looking at main effects of condition as well as interactions (parent gender, parent race/ethnicity, child age, research mistrust), including relevant covariates from the preliminary analyses. We will examine the resource completion rates (at least 70% complete) in the entire intervention group, as well as in subpopulations (parent gender, parent race/ethnicity, research mistrust, research familiarity), as another measure of feasibility. Finally, open-ended feedback about what was liked most, least, and suggested revisions will be coded into categories and summarized. The feedback will be used to create a list of necessary edits to increase the relevance of the resource for parents overall, and for subpopulations of parents.

Exploratory Analyses. To examine intervention effects on the outcome variables at posttest, multiple regression analyses will be used with condition (intervention; active control) as the independent variable. Pretest scores for each outcome will be included as predictor variables and outcome variable means will be reported as adjusted posttest scores. Analyses will be intent-to-treat. Demographic characteristics found to be non-equivalent between the two groups will be included as covariates in the regression models. In addition, moderator analyses will examine intervention effects for subpopulations (e.g., race/ethnicity, sex, research mistrust) to provide evidence regarding how the impact of the PCT Pocket Guide may potentially vary as a function of these characteristics.

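### The knowledge test may favour the Pocket Guide, because its items are drawn from resource content and no check is planned that the control materials cover them

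*Combined protocol and SAP*

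**What the plan says.** **The measure.** Under Measures, Outcomes, Knowledge, the protocol says: "This measure will be created for the purposes of this study based on the content in the parent resource". The items are "fact-based questions in multiple choice format that assess their knowledge about clinical research". The two examples given concern the meaning of assent and whether a child may stop a trial early. The number of items is not stated.

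**The resources.** Under Procedure, one arm reviews the Pocket Guide. The other reviews "articles and videos compiled from a NIH-supported website (Children and Clinical Studies) into one online resource". The control content is not described further.

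**The term.** The Knowledge paragraph does not name an arm. Under Measures, Implementation, the system records the time that "participants spend with the parent resource (PCT Pocket Guide; active control"), so there the term covers both arms.

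**Timing and analysis.** Of the posttest, the Procedure section says: "This questionnaire will include the same questions and instructions at pretest as well as consumer satisfaction questions". Under Exploratory Analyses in the SAP, "multiple regression analyses will be used with condition (intervention; active control) as the independent variable", with the pretest score as a predictor. The Objectives section describes this part of the trial as "a preliminary test of the Pocket Guide's efficacy for improving outcomes related to knowledge, attitudes, self-efficacy, trust" and further outcomes. The Design section states a superiority framework.

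**The concern.** An achievement test built from one arm's teaching material can reward having seen that material. Control parents may be asked for facts that their materials never presented. A higher score in the Guide arm could then mean that the two resources cover different facts, that the Guide teaches the same facts better, or both. The planned single score cannot separate these.

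What is at stake is the interpretation of one exploratory outcome. A knowledge difference could be reported as preliminary evidence that the Guide teaches better than an NIH-supported alternative when it reflects only how the items were chosen.

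**Working it through.** The documents give no sample size, standard deviation, effect size or significance level, so there is no figure of the plan's own to reproduce. The check has three steps.

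**1. Which resource supplies the items?** The noun in the Knowledge paragraph is singular, the study title speaks of one parent resource, and the Procedure section calls the comparator control materials. These point to the Guide. The Implementation paragraph points the other way by applying the term to both arms. The Guide is the likelier reading, but the text does not settle it.

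**2. Would any planned step catch or remove a coverage advantage?**
- *Pretest adjustment.* The pretest is completed before either resource is opened. A coverage advantage arises afterwards, so adjustment leaves it in place.
- *Randomisation.* It balances the parents. The problem would lie in the instrument.
- *Psychometric checks (SAP, Preliminary analyses).* They address reliability, validity and distributions. A test aligned to one resource can be highly reliable, and no comparison of items with the two resources is described.
- *Shared-content subscore.* None is planned.

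**3. How large could it be?** All inputs here are assumptions. Let f be the share of items covered only by the Guide and g the gain in proportion correct on an item that a parent's resource covers. Let g be the same in both arms (equal teaching), with no gain on uncovered items, no control-only items and full use of both resources. Then

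spurious difference = f × g.

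| f | g = 0.10 | g = 0.20 | g = 0.30 |
|---|---|---|---|
| 0 | 0 points | 0 points | 0 points |
| 0.10 | 1 point | 2 points | 3 points |
| 0.25 | 2.5 points | 5 points | 7.5 points |
| 0.50 | 5 points | 10 points | 15 points |

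To turn this into a chance of a significant result favouring the Guide, assume a standard deviation of 20 points and a two-sided 0.05 test. With n per arm, SE = 20 × √(2/n), and the chance is 1 − Φ(1.96 − difference/SE). For n = 100, SE = 2.83. At f = 0.25 and g = 0.20, 5/2.83 = 1.77, and 1 − Φ(0.19) = 0.42. For n = 50, SE = 4.00, so 5/4 = 1.25, and 1 − Φ(0.71) = 0.24.

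| f (g = 0.20) | Difference | 50 per arm | 100 per arm |
|---|---|---|---|
| 0 | 0 points | 2.5% | 2.5% |
| 0.10 | 2 points | 7% | 10.5% |
| 0.25 | 5 points | 24% | 42% |
| 0.50 | 10 points | 71% | 94% |

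If the items were instead drawn from both resources, a share c could be covered only by the control. The difference would be (f − c) × g, which could go either way. The same item mapping would be needed to know.

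**The case against.** The strongest reply is that no bias has been shown. A tilt exists only if the control materials omit tested facts, and what is visible suggests overlap: the control comes from an NIH-supported site on children and clinical studies, and both example items are general facts about paediatric research. This stands. It limits the point to a possible tilt of unknown size, possibly zero.

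A reader might infer more than the documents support in four ways:
- *That the test is certainly written from the Guide.* The Implementation paragraph uses the term for both arms, so this is an inference.
- *That a positive knowledge result is to be expected even with equal teaching.* In the illustration the chance exceeds one half only at the largest Guide-only share shown, and it is 2.5% with full overlap.
- *That the active control was chosen to make such differences interpretable.* The documents give no reason for the choice.
- *That knowledge has priority because the Objectives section names it first among the efficacy outcomes.* It is analysed under Exploratory Analyses, and the Outcomes section lists likelihood and willingness before it.

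A further reply is that covering more relevant facts is a real merit of a resource, so scoring shared items alone would change the question. This also stands. It is why the full score should be kept and the shared-content result reported beside it. What the reply does not answer is that the full score alone cannot show whether coverage or teaching produced a difference.

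**Conclusion.** The concern holds in a limited form. The knowledge comparison may favour the Guide to the extent that items are covered only by the Guide, and nothing in the plan would reveal or remove this. On the assumptions shown, the spurious difference runs from 0 to 15 percentage points. With a 20-point gain it is 5 points when a quarter of the items are Guide-only. These figures rest on assumed values of f, g, the standard deviation and the number per arm, and incomplete use of the resources would shrink them. The documents do not support the statement that the comparison is biased.

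The analyses under Main Analyses (the AIM, IAM and FIM scores, completion rates and open-ended feedback) do not use the knowledge score as an outcome and are unaffected. The point matters for what may be concluded from a knowledge difference in a feasibility trial, and it is cheap to settle.

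**What to change.** 1. State in the Knowledge paragraph which resource or resources supply the items.
2. Before posttest data are examined by arm, and before any item is dropped on psychometric grounds, have existing staff tag each item as covered by both resources, by the Guide only or by the control only. Report the number in each class.
3. Keep the full-score comparison. Add to Exploratory Analyses the same pretest-adjusted comparison on shared-content items and, separately, on Guide-only items. Where imputation is used, it is already planned at item level, so the subscores can be formed from the imputed items.
4. Add one sentence on interpretation: better teaching is claimed only if the shared-content comparison supports it; otherwise the conclusion is limited to learning of Guide content.

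This needs no new participants or data. The cost is a small mapping task and a few sentences in the SAP. The shared-content score will be shorter and less reliable than the full score, so its comparison will be less precise and a null result on it should be read with that in mind.

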Preliminary analyses. Psychometric analyses will be conducted to examine the reliability, validity, and distributions of key variables and scales. Handling variables with poor reliability or validity will include modification or elimination of such variables from the analysis data sets. Variables with noticeably skewed distributions will be transformed or categorized to reduce the impact of non-normality on subsequent analyses. Descriptive statistics will also be conducted to examine the distributions, correlations, means, and standard deviations of the outcome variables. Preliminary analysis will include a test of equivalency between the intervention and control groups on demographic characteristics and baseline levels of primary outcome variables using chi-squared analyses for categorical variables and t-tests for continuous variables. Any characteristics that are nonequivalent will be added as covariates in the main analyses. Depending on the level of missingness, missing data will be multiply imputed at the item level. The imputation model will be estimated using the PROC MI procedure in SAS and will include all outcome items and demographic characteristics that will aid in estimating missing data values. Main analyses will be conducted on each of the imputed datasets.

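### Outcomes may be recoded or dropped with no fixed trigger and no blinding to condition; categorising skewed scores would lose power without need

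*Combined protocol and SAP*

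**What the plan says.** The Statistical Analysis Plan, Preliminary analyses, begins with a general check: "Psychometric analyses will be conducted to examine the reliability, validity, and distributions of key variables and scales". Two rules follow.

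- On weak measures: "Handling variables with poor reliability or validity will include modification or elimination of such variables from the analysis data sets".
- On shape: "Variables with noticeably skewed distributions will be transformed or categorized to reduce the impact of non-normality on subsequent analyses".

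Both are written as commitments. Neither comes with a skewness or reliability threshold, a named transformation, cut-points, or a list of the variables covered. The section does not say whether the checks use pretest data, pooled data or data split by condition.

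AIM, IAM and FIM are posttest scales of four items each, scored 1 to 5 (Measures, Consumer Satisfaction). Under Main Analyses they "will first be examined through descriptive statistics", against this criterion: "Group mean scale scores greater than 3.0 will indicate more than a moderate amount of acceptability, appropriateness, and feasibility for each resource". After that, "ANCOVAs will be used to compare AIM, FIM, and IAM scores looking at main effects of condition as well as interactions". Exploratory Analyses uses multiple regression with the pretest score as a predictor and reports adjusted posttest means. No model is given for a categorised outcome, and no back-transformation is given for a transformed one.

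**The concern.** Three things are at stake.

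1. **Power.** ANCOVA and regression do not need an unskewed outcome. What matters is the behaviour of the residuals, and a difference in means tolerates a good deal of skew at moderate sample sizes. Cutting a score into categories throws away information to solve a problem that may not exist.
2. **Outcome selection.** The triggers are left to judgement and no blinding is described. The plan therefore does not prevent the form of an outcome, or whether it is kept at all, from being settled once results by condition can be seen. AIM, IAM and FIM are collected only at posttest, so their shape can be judged only on outcome data.
3. **The 3.0 criterion.** It has meaning only on the 1 to 5 metric. Recoding is placed in the preliminary stage, and nothing says that raw scores are kept for the criterion.

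**Working it through.** **Inputs.** From the documents: four-item scales scored 1 to 5, the 3.0 criterion, and 1:1 allocation. The documents give no sample size, alpha, power, effect size or SD, so there is no planned figure to reproduce. Assumed here: two-sided alpha 0.05, a latent shift of 0.5 SD, and 40 to 175 parents per arm, with 64 per arm as the reference.

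**Step 1: simulation of a skewed scale.** Each item has a normal latent value with variance 1 and between-item correlation 0.7, cut at -1.6, -1.0, -0.2 and 0.8 into scores 1 to 5; the scale score is the mean of four items. Latent means of 1.0 and 1.6 give control means of 4.44 (SD 0.64) and 4.75 (SD 0.43). With no effect, skewness is about -1.3 and -2.2. There were 8,000 runs per setting. Raw and transformed scores were compared by t-test, and split scores by a two-proportion test.

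**Step 2: is the rule needed for validity?** With no effect and 40 to 175 per arm, the raw-score t-test rejected in 0.046 to 0.051 of runs. The simulation standard error at 0.05 is √(0.05 × 0.95 / 8,000) = 0.0024, so this is in line with the nominal level.

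**Step 3: power at 64 per arm.**

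| Version | Control mean 4.44 | Change | Control mean 4.75 | Change |
|---|---|---|---|---|
| Raw score | 79.5% | – | 65.0% | – |
| ln(6 − x) | 81.8% | +2.3 | 68.4% | +3.4 |
| Squared | 80.8% | +1.3 | 66.6% | +1.6 |
| Median split | 70.5% | −9.0 | 64.2% | −0.8 |
| Cut at 4 | 47.8% | −31.7 | 20.8% | −44.2 |

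The monotone transformations cost nothing. Categorising cost from about 1 point to 44, depending on where the cut fell. The 0.8-point loss is close to simulation error, since √(0.65 × 0.35 / 8,000) is about 0.5 point on each figure.

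**Step 4: choosing among versions.** With no effect, taking the smallest p-value of these five versions of one outcome gave a type I error of 0.105 to 0.120 across all sizes and both control means, against a nominal 0.05.

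**Step 5: the 3.0 criterion on other metrics.** The highest possible score is 5.

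- Square root: maximum √5 = 2.24.
- ln(x), or ln(6 − x) with its direction reversed: maximum ln 5 = 1.61.
- 0/1 split: maximum 1.
- Squared: 3.0 corresponds to a raw score of √3 = 1.73.

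Under the first three, a mean above 3.0 is impossible. Under squaring, the bar falls well below the middle of the raw scale.

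**Limits.** The tests are unadjusted: no pretest covariate and no imputation. In Steps 2 and 4 both arms have the same distribution.

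**The case against.** The strongest reply is that the plan says less than a reader might infer from it. Several stronger readings are not supported.

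- **That the plan breaks its own 3.0 criterion.** Main Analyses applies the criterion first, as a descriptive group mean, and the skew rule is aimed at later analyses. A descriptive mean needs no normality, so the natural reading is that raw means are used. The criterion fails only if recoding comes before that step, which the text neither states nor excludes.
- **That transforming costs power.** Step 3 shows small gains. The loss belongs to categorising alone.
- **That the loss can be read from a median split of a normal score**, which keeps 2/π = 64% of the information. The rule reaches only skewed variables and mentions neither a median split nor two groups. For skewed scores the loss may be much smaller or much larger.
- **That the team will see results by arm and choose.** This would be inferred from silence. What can be said is that nothing in the plan prevents it.
- **That AIM, IAM and FIM will trigger the rules.** The documents give no distribution for them, and Consumer Satisfaction credits them with good discriminant validity and reliability. Removal is a greater risk for the knowledge test built for this study and for the adapted scales.

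It is also fair that this is a feasibility trial, that effects on knowledge, attitudes and trust are labelled exploratory, and that the 70% completion measure is untouched.

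All of this limits the consequence. It does not supply the missing triggers, variable list or blinding, nor a model for the categorised outcomes that the rule may produce.

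**Conclusion.** The point holds in a limited form. The SAP commits to recoding or removing variables on undefined grounds, with no safeguard that keeps those decisions apart from condition.

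The power loss comes from categorising and is avoidable, because the raw-score test behaved properly under marked skew. The range of about 1 to 44 points belongs to the assumed 64 per arm, 0.5 SD latent shift and two simulated ceilings. The type I error of about 0.11 to 0.12 for one outcome is what the plan leaves room for if the best of five particular versions were taken; it does not predict conduct. Harm to the 3.0 criterion is conditional on the order of steps. The change should be made before posttest data are opened, but the exploratory status of most affected effects keeps this from being a critical flaw.

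**What to change.** Amend the SAP as follows.

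1. Name the raw scale scores as the analysis variables for the ANCOVAs and regressions, with heteroscedasticity-robust or bootstrap standard errors.
2. Confine transformed or categorised versions to sensitivity analyses, naming the transformation or cut-points in advance.
3. State that 3.0 applies to raw group means of AIM, IAM and FIM, and keep those three scales as published.
4. Take any change to a multi-item scale against a pre-set rule, such as a stated floor for Cronbach's alpha. Use pretest data, or pooled data blind to condition for measures collected only at posttest. Single-item outcomes (likelihood, fear, familiarity) have no alpha and should stay outside this rule.
5. List the variables covered and report every pre-specified outcome, with a caveat where reliability is low.

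The cost is SAP wording and a standard-error option in the SAS code. The small downside is that low-reliability scales are still reported.

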The study type is interventional and the study model is parallel assignment with a 1:1 allocation ratio and superiority framework to examine the feasibility of the PCT Pocket Guide. The randomized controlled trial will be conducted online at two time points: 1) baseline/pretest and 2) posttest (two weeks after pretest). The study questionnaires will be programmed into an online data collection system. The resources (intervention and active control) will also be completed online by participants. Participants will be randomized, stratifying based upon race/ethnicity (white and not Hispanic/Latino; nonwhite and/or Hispanic/Latino) to one of two conditions: 1) intervention (access to PCT Pocket Guide) or 2) active control (access to control materials compiled from a NIH-supported website). Participants are randomized and enrolled based on: 1) time study forms (i.e., consent) were completed, 2) confirmation of email addresses, 3) their reported demographics collected in the eligibility screener questions, 4) address verification, and 5) indication that they learned about the study from one of the targeted school districts. One of the Co-Principal Investigators will generate the allocation sequences using a random number generator in Excel, assign participants to condition (either intervention or active control) according to those sequences, and enroll participants in the study. The allocation sequence will be stored in a folder on a secure, password-protected server. All participants will be assigned a unique ID number that will be associated with their data (questionnaires; resource use) in place of their name. All personally identifiable information (PII) will be saved on iRT's password protected server, and kept separate from data.

Methods:

Sample and Recruitment.

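### Covariates are picked by baseline significance tests and the race/ethnicity stratum is not fixed in the condition comparisons, which gives up precision without inflating false positives

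*Combined protocol and SAP*

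**What the plan says.** The SAP paragraph on preliminary analyses compares the arms on demographics and on pretest values of the primary outcomes, "using chi-squared analyses for categorical variables and t-tests for continuous variables". It gives no significance level. The rule follows: "Any characteristics that are nonequivalent will be added as covariates in the main analyses".

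Under Main Analyses, "ANCOVAs will be used to compare AIM, FIM, and IAM scores looking at main effects of condition as well as interactions". The interaction terms and the covariates are given as "parent gender, parent race/ethnicity, child age, research mistrust), including relevant covariates from the preliminary analyses".

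Under Exploratory Analyses there are two separate provisions. The first is unconditional: "Pretest scores for each outcome will be included as predictor variables and outcome variable means will be reported as adjusted posttest scores". The second is conditional on the baseline tests and concerns demographics only: "Demographic characteristics found to be non-equivalent between the two groups will be included as covariates in the regression models". Moderator analyses, with race/ethnicity and research mistrust among the examples, are planned in addition.

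The Design section of the protocol says "Participants will be randomized, stratifying based upon race/ethnicity (white and not Hispanic/Latino; nonwhite and/or Hispanic/Latino", and that a Co-Principal Investigator will "generate the allocation sequences using a random number generator in Excel". It does not mention blocking. The Measures section places AIM, IAM and FIM in the consumer satisfaction questionnaire, which is given at posttest only.

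**The concern.** Allocation is random, so a baseline difference between the arms arises by chance, and a non-significant test does not show that the arms are equivalent. Adjustment helps when a covariate predicts the outcome, and these tests do not examine that. A strongly prognostic variable that happens to be balanced is left out, and an irrelevant one that happens to be imbalanced goes in.

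The rule bears most on the AIM, IAM and FIM ANCOVAs. These scales rate a resource after it has been reviewed, so they have no pretest score of their own. Other pretest scores (attitudes, familiarity, knowledge, self-efficacy) are collected, but they can enter as covariates only if the arms happen to differ on them. The stratification factor is in a similar position. The design balances it on purpose, which makes it less likely to be flagged, and neither covariate rule names it.

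Two things are at stake: precision that is already paid for in collected data, and a model that can be written down before the data are seen. At present neither the threshold for non-equivalence nor the set of relevant covariates is defined.

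**Working it through.** The documents state no sample size, power, significance level, effect size or SD, so there is no planned figure to reproduce. What follows is illustrative.

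**Inputs from the documents:** 1:1 allocation; a two-level stratum; covariates added only after a baseline test; posttest-only AIM, IAM and FIM; each exploratory outcome's pretest score always in its model.

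**Assumptions:** 50 per arm, true difference d = 0.5 SD, two-sided 0.05 for both the baseline test and the outcome test, and one covariate explaining a share R² of outcome variance (R² = correlation squared).

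**Step 1. How often the rule selects.** Under randomisation a baseline test at 0.05 is significant in about 5% of trials, however prognostic the variable is. Simulation gave 4.8% to 5.2%. At least one of k independent tests is significant with probability 1 − 0.95^k: 1 − 0.95^5 = 0.226 and 1 − 0.95^10 = 0.401. The plan states no k, so this shows only how unpredictable the final model is.

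**Step 2. Power if the covariate is always included.** The noncentrality is d / √(2/n) / √(1 − R²). Without the covariate it is 0.5 / √(2/50) = 0.5 / 0.2 = 2.50, which gives 69.7% power from the noncentral t. With it:

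- R² = 0.02: 2.50 / √0.98 = 2.525, power 70.6%
- R² = 0.04: 2.50 / √0.96 = 2.552, power 71.4%
- R² = 0.10: 2.50 / √0.90 = 2.635, power 74.2%
- R² = 0.30: 2.50 / √0.70 = 2.988, power 84.1%

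**Step 3. The plan's rule against always adjusting.** Simulation with 10,000 trials per cell and a continuous covariate (Monte Carlo standard error about 0.5 points for power and 0.2 points for the false-positive rate):

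| R² | Power, never | Power, rule | Power, always | False positives, rule |
|---|---|---|---|---|
| 0.02 | 69.4% | 69.5% | 69.9% | 4.6% |
| 0.04 | 69.5% | 69.5% | 70.7% | 4.6% |
| 0.10 | 69.6% | 70.2% | 74.2% | 4.5% |
| 0.30 | 69.1% | 70.2% | 83.6% | 4.3% |

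The rule tracks never adjusting. Further simulations with total N from 60 to 200, with the effect set for about 80% unadjusted power, show the same pattern: 79-80% under the rule versus 82-83% at a correlation of 0.3 (R² = 0.09), and 79-81% versus 88-90% at 0.5 (R² = 0.25).

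**Step 4. The stratum.** If randomisation within strata is blocked and the stratum is omitted, the standard error is too large by a factor 1/√(1 − R²), and the false-positive rate is 2 × [1 − Φ(1.96/√(1 − R²))]. For correlations of 0.1, 0.2, 0.3 and 0.5 between stratum and outcome, the standard error is overstated by 0.5%, 2%, 5% and 15%, and the false-positive rate is 4.9%, 4.6%, 4.0% and 2.4%. In simulations with N = 100 and a 50/50 stratum, the stratum was flagged in no trial with blocks of 4. With simple randomisation within strata it was flagged in about 5% of trials, and the rule's false-positive rate was 4.0% to 5.0%.

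**The case against.** The strongest reply is that this is a feasibility trial. Its first criteria are descriptive: group means above 3.0 on AIM, IAM and FIM, and completion of at least 70%. No covariate choice affects either. Efficacy is labelled exploratory, and the errors described here are conservative. No document figure supports a covariate with R² as high as 0.30 for a two-level race/ethnicity variable, or for baseline scales predicting satisfaction with a web resource. At R² of 0.02 to 0.04 the loss is about one percentage point. All of this stands, and it limits the weight of the point.

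A reader might also infer three stronger things that the documents do not support.

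- *That prognostic pretest scores are dropped.* In the exploratory regressions each outcome's own pretest score is included without condition, so the loss there is confined to the stratum and other demographics, over and above what the pretest score already explains. AIM, IAM and FIM have no own pretest score to drop.
- *That the stratification factor is excluded by construction.* Race/ethnicity is named in the ANCOVA interactions and among the moderators, and a standard interaction model carries its main effect. What is missing is a statement that the main effect of condition comes from such a model. Near-certain failure to be flagged also needs blocking or a similar device, which the plan does not describe.
- *That the inference is invalid.* In the calculations above the rule's false-positive rate is at or below nominal. A baseline covariate that enters because of chance imbalance does not by itself bias a randomised comparison.

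The reply does not defend the rule itself. It is written into the SAP, it selects on the wrong criterion, and replacing it needs no new data.

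**Conclusion.** The point holds as one that should be fixed. Covariate choice rests on baseline tests between randomised arms, at an unstated threshold, for the AIM, IAM and FIM ANCOVAs and for demographics in the exploratory regressions. The race/ethnicity stratum is not fixed for the main effect of condition in either set of models.

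The consequence is lost precision and standard errors that are correct or somewhat too wide. Under the stated assumptions the power given up runs from about 1 point or less (R² 0.02-0.04), through about 4 points (0.10), to about 14 points (0.30). Where in that range the trial lies cannot be settled from the documents, because sample size, SD and correlations are absent. The upper end needs a strongly prognostic covariate, which is more than the plan gives reason to expect from the stratum alone. The descriptive feasibility criteria are untouched.

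**What to change.** Before outcome data are seen:

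1. Delete the baseline-test rule in both places, that is, under Preliminary analyses and for demographics under Exploratory Analyses.
2. State that every model comparing conditions contains condition and the race/ethnicity stratum, and say which model supplies the main effect of condition.
3. Keep each outcome's own pretest score in the exploratory regressions, as already planned.
4. For the AIM, IAM and FIM ANCOVAs, name a short list of baseline scores already collected, chosen for expected prognostic value. Pretest research mistrust (already named as a moderator) and pretest attitudes are examples. The documents do not show which scores predict these scales, so the choice is the study team's.
5. Report the baseline table descriptively, without p-values.

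The cost is about two sentences of SAP wording and a few degrees of freedom. No new data are needed.
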